### 17.1.9. CHANGES FROM DB BASELINE AND FROM OL BASELINE IN SHAPS TOTAL SCORE AT EACH SCHEDULED VISIT

The Snaith-Hamilton Pleasure Scale (SHAPS) is a subject-reported questionnaire having a 14-item scale that assesses 4 domains of hedonic experience: interest/pastimes, social interaction, sensory experience, and food/drink. Each of the items has a set of four response categories: strongly disagree, disagree, agree, or strongly agree, with either of the Disagree responses receiving a score of 1 and either of the Agree responses receiving a score of 0. Thus, the SHAPS total score is scored as the sum of the 14 items and ranges from 0 to 14. A higher SHAPS total score indicated higher levels of present state of anhedonia.

SHAPS is assessed at these study visits: Visit 1E (coinciding with Visit 9 of SEP380-301), Visit 4E, Visit 6E, Visit 8E, Visit 10E, Visit 12E, and Visit 14E.

The DB Baseline and OL Baseline SHAPS total score will be derived as described in [Section 7.2](#). The change from DB Baseline and OL Baseline in SHAPS total score will be derived as described in [Section 17.1.9](#).

The observed values of SHAPS total score at both the DB Baseline and the OL Baseline, and at each scheduled OLE study visit (starting from Visit 1E) and LOCF, will be summarized descriptively.

Changes from DB Baseline in SHAPS total score will be summarized for each scheduled OLE study visit (starting from Visit 1E) and LOCF. Changes from OL Baseline will be summarized for each scheduled post-OL Baseline extension study visit (starting from Visit 4E) and LOCF.

## 17.2. MISSING DATA

Any individual missing item in any scale will not be imputed.

For derived scores that depend on more than one individual item (e.g., MADRS total score, EQ-5D-5L index score), if one or more items are missing at a visit, the derived score will be set to missing. The corresponding change from DB Baseline or OL Baseline value at a given time point will be set to missing if the DB Baseline or OL Baseline derived score is missing or if the derived score at that time point is missing.

For MADRS response compared to DB Baseline, any subject with a missing MADRS total score at DB Baseline or at any scheduled OLE study visit (starting from Visit 1E) or LOCF will have their MADRS response set to missing for that time point.

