### 8.3. MISSING DATA

Individual missing items in any rating scale will not be imputed in any analysis. When calculating a total score, subscale score, or any summary scores based on more than one item, if one or more items are missing at a visit, then the associated summary score will be set to missing. For additional details, see the individual scale description sections.

- Handling of missing efficacy data, if any, is described in [Section 17.2](#).
- Handling of missing safety data, if any, is described in [Sections 18.1.1](#) and [18.6](#).
- See [APPENDIX 2](#) for details of handling incomplete/missing dates.

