#### **17.1.6. CHANGES FROM DB BASELINE AND FROM OL BASELINE IN QIDS-SR16 TOTAL SCORE AT EACH SCHEDULED VISIT**

The Quick Inventory of Depressive Symptomatology – Self Report (QIDS-SR16) is a 16-item subject-reported depression symptom severity questionnaire. Each item is rated 0 to 3. The scoring of the QIDS-SR16 converts responses to 16 separate items into the 9 DSM-IV symptom criterion domains. The 9 domains are: sad mood (Item 5), concentration (Item 10), self-criticism (Item 11), suicidal ideation (Item 12), interest (Item 13), energy/fatigue (Item 14), sleep disturbance (early/middle/late insomnia or hypersomnia) (Items 1 to 4), decrease/increase in appetite/weight (Items 6 to 9), and psychomotor agitation/retardation (Items 15 and 16). For symptom domains that consist of more than one item, the highest score among the items relevant to the given domain is taken. The total score will be equal to the sum of the 9 domains and ranges from 0-27 with higher scores indicating greater severity.

QIDS-SR16 is assessed at these study visits: Visit 1E (coinciding with Visit 9 of SEP380-301), Visit 4E, Visit 6E, Visit 8E, Visit 10E, Visit 12E, and Visit 14E.

The DB Baseline and OL Baseline QIDS-SR16 total score will be derived as described in Section 7.2. The change from DB Baseline and OL Baseline in QIDS-SR16 total score will be derived as described in Section 17.1.6.

The observed values of QIDS-SR total score at both the DB Baseline and the OL Baseline, and at each scheduled OLE study visit (starting from Visit 1E) and LOCF, will be summarized descriptively.

Changes from DB Baseline in QIDS-SR total score will be summarized for each scheduled OLE study visit (starting from Visit 1E) and LOCF. Changes from OL Baseline will be summarized for each scheduled post-OL Baseline extension study visit (starting from Visit 4E) and LOCF.

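### The item-level missing-data rule in SAP 8.3 and 17.2 discards some QIDS-SR16 totals that the highest-item scoring in SAP 17.1.6 leaves exactly determined (minor)

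*SAP*

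**What the plan says.** **The general rule.** SAP 8.3 covers any total, subscale or summary score built from more than one item: "if one or more items are missing at a visit, then the associated summary score will be set to missing". SAP 17.2 repeats it for the effectiveness scales ("if one or more items are missing at a visit, the derived score will be set to missing") and adds "Any individual missing item in any scale will not be imputed". The MADRS total and the EQ-5D-5L index are named there only as examples, so the QIDS-SR16 total is covered.

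**The QIDS-SR16 scoring.** SAP 17.1.6 rates each item 0 to 3, converts the 16 items to nine domains and sums the domains to a total of 0 to 27. Six domains have one item each. The other three are sleep (Items 1-4), appetite/weight, listed as "decrease/increase in appetite/weight (Items 6 to 9", and psychomotor change (Items 15-16). For these, "For symptom domains that consist of more than one item, the highest score among the items relevant to the given domain is taken".

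**No exception.** SAP 8.3 refers to the individual scale sections for further detail, but 17.1.6 has no missing-item rule. Other sections do adapt the rule to the scoring. In 18.6.3 only the seven AIMS items that enter the total trigger missingness, and in 18.6.4 only BARS Items 1 to 3 do.

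**The concern.** A rule that voids a score for any blank suits a scale in which every item is added, such as MADRS or HAM-A, because there any blank leaves the sum unknown. It fits a domain maximum less well. Ten of the 16 QIDS-SR16 items sit in domains scored by their highest item, and a blank among them sometimes cannot alter the result. The total is then known, and the SAP still discards it.

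The protocol's objective on subject-reported depression severity (Protocol 5.3) rests on this scale. It is assessed at seven visits (1E, 4E, 6E, 8E, 10E, 12E and 14E), and 64 subjects were enrolled (SAP 4.4). A voided post-baseline total drops out of the by-visit table, and if it was the last one, the LOCF endpoint falls back on an older value (SAP 7.3). A voided Visit 1E total has a wider effect. Under SAP 7.2 the OL Baseline becomes the last non-missing earlier measurement. If there is none, every change from OL Baseline for that subject is missing under 17.2.

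**Working it through.** **Step 1. Reproduce the stated range.** Single-item domains are Items 5, 10, 11, 12, 13 and 14, which makes 6. Multi-item domains have 4, 4 and 2 items. Items: 6 + 4 + 4 + 2 = 16. Domains: 6 + 3 = 9. Maximum total: 9 x 3 = 27, as stated. Summing all items would give 16 x 3 = 48, so the total does rest on domain maxima.

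**Step 2. When does one blank leave the domain score fixed?** These are counts of possible answer patterns, not expected frequencies.

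- *Another item already scores 3.* In a four-item domain the other three items have 4^3 = 64 patterns, of which 3^3 = 27 contain no 3. That leaves 64 - 27 = 37 of 64 fixed. In the two-item domain it is 1 of 4.
- *Opposite directions in appetite/weight.* Assume Items 6-9 form two decrease/increase pairs, one for appetite and one for weight, with at most one item of a pair above 0. Each pair then has 4 + 3 = 7 consistent patterns, 49 in all. Leave one item blank. If its partner is above 0 (3 x 7 = 21 patterns), the blank must be 0. If its partner is 0 (4 patterns of that pair), the domain is fixed only when the other pair contains a 3 (2 of 7), giving 4 x 2 = 8. Total: 21 + 8 = 29 of 49. With the first condition alone it would be 7 + 6 x 2 = 19 of 49.

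In the remaining patterns the domain score is only bounded, and setting it to missing is reasonable.

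**Step 3. Totals lost per visit.** Let q be the probability that an item is blank, independently across items. The documents give no value, so q is an assumption shown as a range.

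- Current rule: L = 1 - (1 - q)^16.
- Floor for any rule that works at domain level, voiding a total only when some domain has no answered item: F = 1 - (1 - q)^6 x (1 - q^4)^2 x (1 - q^2).
- L - F is therefore a ceiling on what could be recovered.

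At q = 1%, L = 1 - 0.99^16 = 14.85% and F = 5.86%.

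| q | L (current rule) | F (floor) | Ceiling L - F | L and F, of 64 subjects |
|---|---|---|---|---|
| 0.1% | 1.59% | 0.60% | 0.99 points | 1.0 and 0.4 |
| 0.5% | 7.71% | 2.97% | 4.74 points | 4.9 and 1.9 |
| 1% | 14.85% | 5.86% | 8.99 points | 9.5 and 3.8 |
| 2% | 27.62% | 11.45% | 16.17 points | 17.7 and 7.3 |

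The last column takes all 64 enrolled subjects as assessed, for scale only.

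**Step 4. Where a rule limited to determined totals would fall.** It recovers only the fixed patterns of Step 2, so its loss lies between F and L. The exact position depends on how subjects answer, which the documents do not show.

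**The case against.** The strongest defence is that a uniform, prespecified complete-item rule is transparent and easy to program, and that a blank item may be the highest in its domain. A maximum depends on every item it is taken over, so treating many of these totals as missing is sound. QIDS-SR16 is also captured by eCOA (Protocol 16.2, Table 6), which may not permit blanks. Protocol 11.3.4 leaves administration and recording to the Study Reference Manual. If blanks are blocked, nothing is lost. The scale is one of several effectiveness measures, MADRS and CGI-BP-S are collected more often, and SAP 7.6 rules out inference.

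All of this limits the point. None of it justifies discarding a total that is already determined.

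Two stronger readings are tempting and should not be drawn.

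- *That properly completed forms leave one item of each decrease/increase pair blank, so up to all totals are lost and the tables could be empty.* SAP 17.1.6 gives every item a rating of 0 to 3, and Protocol 11.3.4 speaks of 16 separate items. On a plain reading, a subject with no increase answers 0. Nothing in the documents says the opposite item is skipped or stored as blank.
- *That the remedy is to take the highest answered item whatever is blank.* This treats the blank as no worse than the answered items. It can understate a domain by up to 3 points, or 9 of 27 if all three multi-item domains are affected, and always towards lower severity. The floor F counts such totals as recovered, so it overstates the valid gain.

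**Conclusion.** The point holds in limited form. As written, SAP 8.3 and 17.2 void the QIDS-SR16 total for any one blank among 16 items, and under the scoring in 17.1.6 some of those totals are exactly determined. The adapted rules for AIMS and BARS suggest an omission rather than a deliberate choice.

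The loss cannot be stated from the documents. At assumed independent blank rates of 0.1% to 2% per item it runs from 1.6% to 27.6% of totals per visit, and only part of that is recoverable. If blanks cluster within subjects, fewer totals are lost at the same rate. If the eCOA forces an answer, none are. The use of opposite directions also assumes that Items 6-9 are two decrease/increase pairs, which should be checked against the form.

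Severity is minor: the summaries are descriptive and the primary safety endpoints do not use this scale.

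**What to change.** Add to SAP 17.1.6, before database lock, wording such as:

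> A multi-item domain score is derived despite a blank item when the blank cannot change the domain maximum: another item in the domain scores 3, or, in appetite/weight, the opposite-direction item of the same pair is above 0, so that the blank is taken as 0. Otherwise the domain score and the total are missing. For QIDS-SR16 this replaces the item-level rule in Sections 8.3 and 17.2.

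Apply the same derivation to the OL Baseline and to every visit. Confirm how the eCOA stores the opposite-direction items and whether it accepts blanks. Because SAP 7.2 takes the DB Baseline directly from the SEP380-301 datasets, confirm that it was derived in the same way, so that changes from DB Baseline compare like with like.

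The cost is a short SAP addition and a small programming change. If there are no blanks, no result changes. One side effect should be visible to readers. Each recovered total is exact, given consistent answers on the paired items, but recovery depends on those answers and favours subjects with high domain scores. The pull on a visit mean is the recovered share times the gap between recovered and fully completed forms, so a table footnote should give the number of totals recovered at each visit.

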## 18. SAFETY OUTCOMES

Unless otherwise specified, the safety summary tables will include the following columns: PBO-SEP, SEP-SEP, and ALL EXT (all rollovers from SEP380-301).

All analyses of the safety outcomes will be based on the Safety Population, by the actual treatment groups.

### 18.1. ADVERSE EVENTS

Adverse Events (AEs) and pre-treatment events will be coded using MedDRA central coding dictionary, Version 22.0.

The concept of “pre-treatment events” only applies to study SEP380-301. Pre-treatment events are untoward medical occurrences that started prior to the first dose of study medication in SEP380-301.

Adverse events of study SEP380-301 are untoward medical occurrences that started at the same time of or after the first dose of study medication in SEP380-301, but before the first dose of OLE study medication in SEP380-303. These events will be recorded in the SEP380-301 databases.

Adverse events (AEs) of the SEP380-303 extension study are untoward medical occurrences that started at the same time of or after the first dose of the OLE study drug. These events will be recorded in the SEP380-303 database.

AEs (and pre-treatment events) that started in study SEP380-301 and are ongoing at the time of subject rollover will be re-entered into the SEP380-303 database and continue to be followed. These events will not be included in any AE summary table of SEP380-303. They will only be listed in a separate data listing.

Whenever available, the time information should be accounted for to determine if a record in the SEP380-303 AE database belongs to study SEP380-301 or SEP380-303. In the case where time is not available, untoward medical occurrences that started prior to the day of the first OLE dose will be considered to belong to study SEP380-301; those that started after the day of the first OLE dose will be considered to belong to study SEP380-303. Events that started on the same day of the first OLE dose will be assigned to study SEP380-301 or SEP380-303 depending on whether this AE record also exists in the SEP380-301 database (based on a comparison of subject ID, verbatim term, AE start date (and time if available), severity, and seriousness).

See [APPENDIX 2](#) for handling of partial dates for AEs.

Overall summary of the incidence of all AEs, study medication-related AEs, severe AEs, serious AEs, AEs leading to discontinuation from study, AEs leading to death, and AEs of special interest (AESI) will be provided by the actual treatment groups.

Listings will be provided for all AEs, study medication-related AEs, severe AEs, serious AEs, AEs leading to discontinuation from the study, AEs leading to death, and AEs of special interest (AESI). A listing of SEP380-301 events (pre-treatment events and AEs) present in the SEP380-303 database will also be presented. When complete event start date and complete event end date are available, duration of AEs from SEP380-301/303 and pre-treatment events from SEP380-301 will be calculated as: event end date – event start date + 1. Duration will be presented in data listings.

For all summaries, each subject will be counted only once within each category (e.g., an AE type, a severity level, a relationship category, a SOC, and a PT). If not otherwise specified, all summaries will present the number and percentage of subjects as well as the number of events. For summaries by SOC and PT, AEs will be sorted by SOC based on the internationally agreed order (see [APPENDIX 4](#)) and then by PT in decreasing frequency in the “ALL EXT” column. For summaries by SOC, and PT, AEs will be sorted by SOC based on the internationally agreed order and then by PT in decreasing frequency in the “ALL EXT” column.

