#### 18.1.2. AEs LEADING TO DISCONTINUATION FROM STUDY

AEs leading to discontinuation from the study are those AEs with "Caused Study Discontinuation" = "Yes" on the "Adverse Events" CRF form for subjects with reason for discontinuation as AE on the Study Disposition CRF page or AE action taken = "Drug Withdrawn".

AEs leading to discontinuation from the study will be summarized by SOC and PT. A listing of AEs leading to discontinuation from the study treatment period will be presented.

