#### 18.1.3. SERIOUS ADVERSE EVENTS (INCLUDING ADVERSE EVENTS LEADING TO DEATH)

SAEs are those AEs recorded as "Serious" on the "Adverse Events" CRF form. AEs leading to death are those AEs with "Outcome" = "Fatal" on the "Adverse Events" CRF form.

SAEs (including AEs leading to death) will be summarized by SOC and PT. A listing of SAEs (including deaths) will be presented.

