#### **AE start date imputation**

- If year and month (YYYY-MM) of AE start date are known and YYYY-MM = year and month of OLE study med start date, then impute AE start date to be the earlier of (OLE study med start date; full or imputed AE end date [if non-missing]).
- If year and month (YYYY-MM) of AE start date are known and YYYY-MM ≠ year and month of OLE study med start date, then impute AE start date to be YYYY-MM-01.
- If only year (YYYY) of AE start date is known and YYYY = year of OLE study med start date, then impute AE start date to be the earlier of (OLE study med start date; full or imputed AE end date [if non-missing]).
- If only year (YYYY) of AE start date is known and YYYY ≠ year of OLE study med start date, then impute AE start date to be YYYY-01-01.
- If AE start date is completely missing, then impute AE start date to be the earlier of (OLE study med start date; full or imputed AE end date [if non-missing]).

Step 4) Using the full or imputed event dates, assign events into SEP380-301 pre-treatment event, SEP380-301 AE, or SEP380-303 AE as described below.

If both event start date/time and SEP380-303 OLE study med start date/time are available:

- If event start date/time < SEP380-303 OLE study med start date/time, then SEP380-301 pre-treatment event or SEP380-301 AE\*.
- If event start date/time ≥ SEP380-303 OLE study med start date/time, then SEP380-303 AE.

If (event start date is available and time is not available) and/or (SEP380-303 OLE study med start date is available and time is not available):

- If event start date < SEP380-303 OLE study med start date, then SEP380-301 pre-treatment event or SEP380-301 AE\*.
- If event start date > SEP380-303 OLE study med start date, then SEP380-303 AE.
- If event start date = SEP380-303 OLE study med start date and the event record exists in SEP380-301 database§, then SEP380-301 pre-treatment event or SEP380-301 AE\*.
- If event start date = SEP380-303 OLE study med start date and the event record does not exist in SEP380-301 database§, then SEP380-303 AE.

\*The distinction between SEP380-301 pre-treatment event and SEP380-301 AE should be performed as specified in the SEP380-301 SAP.

§Based on a comparison of subject ID, PT, AE start date (and time if available), severity, and seriousness.

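### Under the SAP 18.1 onset rule, a carried-over lead-in event that leads to discontinuation, becomes serious or is fatal on open-label drug can appear in a listing only; a flagged row would close this gap cheaply

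*SAP*

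**What the plan says.** SAP 18.1 treats as a SEP380-303 adverse event only one that starts at or after the first dose of open-label extension (OLE) drug. Events that started in SEP380-301 and are still ongoing at rollover are re-entered in the extension database and followed, but "These events will not be included in any AE summary table of SEP380-303" and "They will only be listed in a separate data listing". The section repeats the commitment to list them: "A listing of SEP380-301 events (pre-treatment events and AEs) present in the SEP380-303 database will also be presented".

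Appendix 2, Step 4 puts the same rule into dates: "If event start date < SEP380-303 OLE study med start date, then SEP380-301 pre-treatment event or SEP380-301 AE". What later happens to the event plays no part in the assignment. Severity and seriousness enter only through the record match, a "comparison of subject ID, PT, AE start date (and time if available), severity, and seriousness", which Step 4 uses when an event starts on the day of the first OLE dose and time is not available.

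The tables that the rule reaches are these:
- The overall summary in SAP 18.1, where the incidence of "serious AEs, AEs leading to discontinuation from study, AEs leading to death, and AEs of special interest (AESI) will be provided".
- SAP 18.1.2, which identifies an AE discontinuation from the study-discontinuation flag on the AE form, "for subjects with reason for discontinuation as AE on the Study Disposition CRF page or AE action taken" being drug withdrawn, and tabulates it by SOC and PT.
- SAP 18.1.3: "SAEs (including AEs leading to death) will be summarized by SOC and PT".

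SAP 3.2.1 names discontinuation due to AEs and SAEs among the primary endpoints. SAP Section 10 separately tabulates reasons for discontinuation, with no restriction on when a causal event began.

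**The concern.** Onset is the natural way to count new events. Discontinuation, a change to serious and death are different: they have their own dates and can fall in the OLE period whatever the onset date. For a carried-over event, the plan counts by the date of onset even when the question is what happened on open-label drug.

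For discontinuation the case can fall between two studies. Inclusion criterion 2 (Protocol 8.1) requires completion of the 6-week lead-in, so a rollover subject is not a lead-in discontinuation. If the carried-over event then ends participation, the extension's AE-discontinuation table omits it as well, while disposition may show the subject under the reason adverse event. The plan asks for no reconciliation of the two counts. For an event that turns serious, the SAE incidence table has no entry.

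The primary objective is long-term safety and tolerability as shown by these rates, so a reader will go to the incidence tables first.

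**Working it through.** **Step 1. Apply the rule to a carried-over event.** Take an event that starts before the first OLE dose and is ongoing at rollover. Step 4 gives SEP380-301 and SAP 18.1 gives listing only. Now let the same record acquire drug withdrawn as action taken, a serious classification or a fatal outcome during the extension. The start date is unchanged, so the assignment is unchanged. Its contribution to the overall summary, the 18.1.2 table and the 18.1.3 table is 0.

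**Step 2. Check that the protocol permits such a case.**
- Exclusion criterion 4 (Protocol 8.2) bars moderate or severe hyperprolactinemia-related AESI from the lead-in; a mild one is not barred.
- Protocol 12.1.3 lists galactorrhea as such an AESI with no severity limit.
- Protocol 13.1 makes discontinuation due to AE mandatory for galactorrhea that has not resolved within 2 weeks of study drug interruption or that recurs with re-challenge.

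Mild galactorrhea present at rollover that later meets that criterion is therefore possible. The documents do not show that it occurred.

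**Step 3. Find the condition for the loss.** Protocol 11.4.1 requires both changes in AEs and new AEs to be recorded. Protocol 12.1.1 allows exacerbation of a pre-existing condition to be an AE. Neither says when a worsening of a carried-over event must be opened as a new record. If a new record is opened with an OLE start date, it is tabulated; if the old record is updated, it is not.

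**Step 4. Compare with the protocol's definition.** Protocol 15.4.3.1 defines a treatment-emergent AE by onset, says that this is what AE will mean from there on, and then applies the term to AEs, SAEs and AEs leading to discontinuation. SAP 18.1 agrees with this, except that for subjects previously on SEP-4199 CR the protocol's period starts at the OL Baseline visit (Day -1) and the SAP's at the first OLE dose (Day 1, the following day), a gap of about one day.

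**Step 5. Size.** The plan gives no figure to reproduce, and the number of affected subjects is not given. The effect per subject is 1/n.

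| Group | n | One subject (percentage points) | Basis |
|---|---|---|---|
| ALL EXT | 64 | 1/64 = 1.56 | SAP 4.4, assuming all enrolled were dosed |
| ALL EXT | 60 | 1/60 = 1.67 | assumption |
| PBO-SEP | 16 to 32 | 1/16 = 6.25 to 1/32 = 3.13 | assumption: one quarter to one half of 64 |
| SEP-SEP | 48 to 32 | 1/48 = 2.08 to 1/32 = 3.13 | remainder of 64 |

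The 64 is a count of enrolled subjects, whom SAP Section 6 defines by signed consent. AE rates use the Safety Population (SAP 6.1), which requires at least one dose and whose size is not stated. As an illustration, a tabulated 0/64 (0.0%) would read 1/64 (1.6%) with one such subject, and 3/64 (4.7%) would become 4/64 (6.25%).

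**The case against.** A reader might infer that SAP 18.1 departs from the protocol, or that two primary endpoints are understated. The documents do not support either reading. As Step 4 shows, the protocol extends its onset definition to SAEs and AEs leading to discontinuation, so a count of lead-in-onset events is an addition to the defined endpoint and not a correction of it. Nor does SAP 18.1.2 promise agreement with disposition: it starts from AEs as 18.1 defines them, and uses the disposition page as one of two alternative conditions. This part of the objection stands in full.

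The loss also depends on how sites enter data, and the CRF completion instructions are not among the documents. Protocol 12.1.1 leaves room for many worsenings to be entered as new AEs. Protocol 12.4.1 requires SAEs arising after first study drug to be reported immediately and recorded consistently with the SAE form. That shows seriousness arising on OLE drug is captured, but it does not say whether a new record is opened. This limits how often the gap can arise; it does not close it.

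Finally, little is hidden. Disposition gives the reasons for discontinuation by group, the carried-over events have their own listing, and in a descriptive study with 64 enrolled a careful reader could find such a case. That is fair, but a listing does not enter an incidence, and the main residual gap is an SAE that is absent from the SAE table.

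**Conclusion.** The point holds as a cheap improvement, minor to moderate in weight. A lead-in-onset event that, under its original record, leads to discontinuation, becomes serious or is fatal on or after the first OLE dose appears in no SEP380-303 AE incidence table, and the AE-discontinuation count can then differ from disposition without explanation. The rule itself is consistent with the protocol, apart from about one day in period start, and should stay.

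The number affected is unknown and may be 0. One subject is about 1.6 percentage points in ALL EXT if all 64 enrolled were dosed, and more in a single group; the per-group figures rest on an assumed split. The conclusion assumes that at least some sites update a carried-over record instead of opening a new one, which the documents neither require nor exclude.

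**What to change.** 1. Keep the onset rule for all existing AE, SAE and AESI tables.
2. In SAP 18.1.2, 18.1.3 and the overall summary, add a separate flagged row by group (PBO-SEP, SEP-SEP, ALL EXT) for lead-in-onset events that lead to discontinuation, or become serious or fatal, on or after the first OLE dose. Do not add this row to the new-onset counts.
3. Reconcile the AE-discontinuation count, including the flagged row, with the disposition table, and footnote any remaining difference.
4. Derive a change to serious as not serious in SEP380-301 and serious in the re-entered record, because Protocol 12.3 does not ask for a date of that change. Match the two records on subject, PT and start date. The existing Appendix 2 match also uses severity and seriousness, so it would fail on exactly the records that changed.

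The cost is SAP wording and one derived flag. No new data are needed: the events are already re-entered, Protocol 12.3 has seriousness, action taken and outcome evaluated for each AE, and Protocol 13.1 has the termination reason, epoch and date of death on the eCRF. The downside is slightly less favourable reported figures, and a row that will include some events that began on placebo or were already reported in SEP380-301. That is why it must stay separate from the new-onset counts.
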